6.2. Part A (q3wk dosing)

6.2.1. Screening Visit (Days –28 to 1)

- Informed consent
- Study eligibility per inclusion/exclusion criteria
- Medical history (see Section 7.1)
- CT or MRI scans (CT/MRI) (see Section 7.2)
- Brain CT or brain MRI
- Confirm availability of adequate archival tumor sample for all subjects, if not available, a fresh biopsy may be collected if medically feasible (see Section 7.1.2 for details of requirements).
- HbA1c and fasting blood glucose (see Section 7.6.3). If HbA1c or fasting glucose is elevated with confirmation upon repeat testing (HbA1c $\geq 6.5\%$, fasting glucose ≥ 126 mg/dL or ≥ 7 mmol/L), the subject should receive glucose management before Cycle 1 (C1) Day 1 or within the first week of C1 (results to be submitted to ICON Results Integration Services [iRIS]).

6.2.2. Baseline Visit (Days –7 to Day 1)

- Physical exam (Section 7.6.4), including height and weight. Measurements of height obtained within the previous 12 months may be used.
- Vital signs (Section 7.6.2)
- Pregnancy test for subjects of childbearing potential (serum or urine pregnancy test; see Section 7.6.5) – must be performed within 3 days prior to administration of LV
- ECOG performance status ([Appendix J](#))
- Complete blood count (CBC) with differential (see Section 7.6.3; results to be submitted to iRIS)

- Serum chemistry panel and liver function tests (see Section 7.6.3; results to be submitted to iRIS)
- Estimated GFR calculation (see Section 7.6.3; results to be submitted to iRIS)
- Collection of concomitant medication information
- Collection of AEs

6.2.3. Treatment Cycle (Day 1 to Day 21)

6.2.3.1. Day 1

If baseline visit activities occur within 3 days prior to C1 Day 1, the following assessments do not need to be repeated at the C1 Day 1 visit:

- Physical exam (Section 7.6.4) including weight
- ECOG performance status ([Appendix J](#))
- CBC with differential
- Serum chemistry panel and liver function tests
- Pregnancy test

Predose

- Confirm subject meets dosing criteria (Section 5.2.3.1)
- Physical exam (Section 7.6.4), including weight
- Pregnancy test (serum or urine) for subjects of childbearing potential (see Section 7.6.5) – does not need to be repeated if it has been performed within 3 days prior to administration of LV
- ECOG performance status ([Appendix J](#))
- Random blood glucose to be collected predose on the day of LV administration (see Section 5.6; results to be submitted to iRIS)
- CBC with differential (see Section 7.6.3; results to be submitted to iRIS)
- Serum chemistry panel and liver function tests (see Section 7.6.3; results to be submitted to iRIS)
- Vital signs (within 60 minutes prior to the start of LV infusion, see Section 7.6.2)
- Blood samples for PK and antitherapeutic antibody (ATA) assessment (C1-Cycle 5 [C5] and every 5 cycles thereafter, see Section 7.3 for time points)
- Blood samples for biomarker assessment (C1 to C6 only; see Section 7.4.1)
- CT/MRI, if required: It is recommended that scans not be scheduled on the dosing day. It is recommended that scans done on the same day as Day 1 of subsequent cycles be completed and reviewed prior to infusion with LV.

- LV administration (within \pm 2 days from Day 21 of the previous cycle; see Section 5.2.3)

Postdose

- Blood samples for postdose PK assessment (C1-C5 and every 5 cycles thereafter, see Section 7.3 for time points)
- Vital signs (within 30 minutes of ending each infusion, and during infusion as clinically indicated see Section 7.6.2)
- If available, submit tumor tissue samples for biomarker analysis as soon as reasonably possible after the subject has met all eligibility requirements (C1 only; see Section 7.4.2)

6.2.3.2. Day 3

- For subjects who receive >200 mg LV per infusion, start mandatory prophylactic G-CSF administration (may begin on Days 2, 3, or 4; see Section 5.4.1)
 - Other subjects who are to receive prophylactic G-CSF should start G-CSF (may begin on Days 2, 3, or 4)
- Blood samples for PK assessment (visit window may be $+1$ day; C1 and Cycle 4 [C4] only, see Section 7.3)

6.2.3.3. Day 8 (\pm 2 days)

- Physical exam (C1 only; see Section 7.6.4)
- CBC with differential (C1 and C2 only; see Section 7.6.3; results to be submitted to iRIS)
- Serum chemistry panel and liver function tests (C1 and C2 only; see Section 7.6.3; results to be submitted to iRIS)
- Blood samples for PK assessment (C1 and C4 only; see Section 7.3 and Table 17 for time points)

6.2.3.4. Day 15 (\pm 2 days)

- Physical exam (C1 only; see Section 7.6.4)
- CBC with differential (C1 and C2 only; see Section 7.6.3; results to be submitted to iRIS)
- Serum chemistry panel and liver function tests (C1 and C2 only; see Section 7.6.3; results to be submitted to iRIS)
- Blood samples for PK assessment (C1 and C4 only; see Section 7.3 for time points)
- Blood samples for biomarker assessment (C1 and C2 only; see Section 7.4.1)

6.3. Part B (q1wk dosing)

6.3.1. Screening Visit (Days -28 to 1)

- Informed consent
- Study eligibility per inclusion/exclusion criteria
- Medical history (see Section 7.1)
- For prostate cancer subjects:
 - Bone scan (see Section 7.2.1)
 - PSA test (see Section 7.6.3)
 - Testosterone measurement (see Section 7.6.3; results to be submitted to iRIS)
- CT/MRI (see Section 7.2)
- Brain CT or brain MRI
- Confirm availability of adequate archival tumor sample for all subjects, if not available, a fresh biopsy may be collected if medically feasible (see Section 7.1.2 for details of requirements).
- HbA1c and fasting blood glucose (see Section 7.6.3). If HbA1c or fasting glucose is elevated with confirmation upon repeat testing (HbA1c $\geq 6.5\%$, fasting glucose ≥ 126 mg/dL or ≥ 7 mmol/L), the subject should receive glucose management before C1 Day 1 or within the first week of C1 (results to be submitted to iRIS).

6.3.2. Baseline Visit (Days -7 to Day 1)

- Physical exam (Section 7.6.4), including height and weight. Measurements of height obtained within the previous 12 months may be used.
- Vital signs (Section 7.6.2)
- Pregnancy test for subjects of childbearing potential (serum or urine pregnancy test; see Section 7.6.5) – must be performed within 3 days prior to administration of LV
- ECOG performance status (Appendix J)
- CBC with differential (see Section 7.6.3; results to be submitted to iRIS)
- Serum chemistry panel and liver function tests (see Section 7.6.3; results to be submitted to iRIS)
- Estimated GFR calculation (see Section 7.6.3; results to be submitted to iRIS)
- Collection of concomitant medication information
- Collection of AEs

6.3.3. Treatment Cycle (Day 1 to Day 21)

6.3.3.1. Day 1

If baseline visit activities occur within 3 days prior to C1 Day 1, the following assessments do not need to be repeated at the C1 Day 1 visit:

- Physical exam (Section [7.6.4](#)) including weight
- ECOG performance status ([Appendix J](#))
- CBC with differential
- Serum chemistry panel and liver function tests
- Pregnancy test
- PSA test for prostate cancer subjects

Predose

- Confirm subject meets dosing criteria (Section [5.2.3.1](#))
- Physical exam (Section [7.6.4](#)), including weight
- Pregnancy test (serum or urine) for subjects of childbearing potential (see Section [7.6.5](#)) – does not need to be repeated if it has been performed within 3 days prior to administration of LV
- ECOG performance status ([Appendix J](#))
- Random blood glucose to be collected prior to dosing on Day 1 of each 21-day cycle (see Section [5.6](#); results to be submitted to iRIS)
- CBC with differential (see Section [7.6.3](#); results to be submitted to iRIS)
- Serum chemistry panel and liver function tests (see Section [7.6.3](#); results to be submitted to iRIS)
- Vital signs (within 60 minutes prior to the start of LV infusion, see Section [7.6.2](#))
- Blood samples for PK and ATA assessment (C1-C5 and every 5 cycles thereafter, see Section [7.3](#) for time points)
- Blood samples for biomarker assessment (C1 to C6 only; see Section [7.4.1](#))
- Review CT/MRI, if applicable (see Section [7.2](#))
- For prostate cancer subjects:
 - Review bone scan, if applicable (see Section [7.2](#))
 - PSA test (see Section [7.6.3](#))
- LV administration (a +2 day dosing window is allowed for subsequent dosing within a cycle; see Section [5.2.3](#)). For nonclinical events requiring skipping a dose(s), must consult with and obtain approval by sponsor medical monitor. At least 7 days must elapse between administrations of LV.

Postdose

- Blood samples for postdose PK assessment (C1-C5 and every 5 cycles thereafter, see Section 7.3 for time points)
- Vital signs (within 30 minutes of ending each infusion, and during infusion as clinically indicated; see Section 7.6.2)
- If available, submit tumor tissue samples for biomarker analysis as soon as reasonably possible after the subject has met all eligibility requirements (C1 only; see Section 7.4.2)

6.3.3.2. Day 3

- Blood samples for PK assessment (visit window may be +1 day; C1 and C4 only, see Section 7.3)

6.3.3.3. Day 8 (± 2 days)

Predose

- Confirm subject meets dosing criteria (Section 5.2.3.1)
- Physical exam (Section 7.6.4) (C1 only)
- CBC with differential (see Section 7.6.3; results to be submitted to iRIS), Cycles 1 and 2 only
- Serum chemistry panel and liver function tests (see Section 7.6.3; results to be submitted to iRIS), Cycles 1 and 2 only
- Random blood glucose in Cycles 1 and 2. Following C2, random blood glucose may be collected as indicated in subjects at risk for hyperglycemia. (see Section 5.6; results to be submitted to iRIS)
- Vital signs (within 60 minutes prior to the start of LV infusion, see Section 7.6.2)
- Blood samples for PK assessment (C1 and C4 only; see Section 7.3 for time points)
- LV administration (a +2 day dosing window is allowed for subsequent dosing within a cycle; see Section 5.2.3). For nonclinical events requiring skipping a dose(s), must consult with and obtain approval by sponsor medical monitor. At least 7 days must elapse between administrations of LV.

Postdose

- Vital signs (within 30 minutes of ending each infusion, and during infusion as clinically indicated; see Section 7.6.2)
- Blood samples for PK assessment (C1 and C4 only; see Section 7.3 for time points)

6.3.3.4. Day 15 (\pm 2 days)

Predose

- Confirm subject meets dosing criteria (Section 5.2.3.1)
- Physical exam (C1 only; see Section 7.6.4)
- CBC with differential (see Section 7.6.3; results to be submitted to iRIS), Cycles 1 and 2 only
- Serum chemistry panel and liver function tests (see Section 7.6.3; results to be submitted to iRIS), Cycles 1 and 2 only
- Random blood glucose in Cycles 1 and 2. Following C2, random blood glucose may be collected as indicated in subjects at risk for hyperglycemia. (see Section 5.6; results to be submitted to iRIS)
- Vital signs (within 60 minutes prior to the start of LV infusion, see Section 7.6.2)
- Blood samples for PK assessment (C1 and C4 only; see Section 7.3 for time points)
- Blood samples for biomarker assessment (C1 and C2 only; see Section 7.4.1)
- LV administration (a \pm 2 day dosing window is allowed for subsequent dosing within a cycle; see Section 5.2.3). For nonclinical events requiring skipping a dose(s), must consult with and obtain approval by sponsor medical monitor. At least 7 days must elapse between administrations of LV.

Postdose

- Vital signs (within 30 minutes of ending each infusion, and during infusion as clinically indicated; see Section 7.6.2)
- Blood samples for PK assessment (C1 and C4 only; see Section 7.3 for time points)

6.4. Part C (monotherapy and pembrolizumab combination)

6.4.1. Screening Visit (Days -28 to 1)

- Informed consent
- Study eligibility per inclusion/exclusion criteria
- Medical history (see Section 7.1)
- CT/MRI (see Section 7.2)
- Brain CT or brain MRI
- Confirm availability of adequate archival tumor sample for all subjects, if not available, a fresh biopsy may be collected if medically feasible (see Section 7.1.2 for details of requirements).
- HbA1c and fasting blood glucose (see Section 7.6.3). If HbA1c or fasting glucose is elevated with confirmation upon repeat testing (HbA1c \geq 6.5%, fasting glucose

≥ 126 mg/dL or ≥ 7 mmol/L), the subject should receive glucose management before C1 Day 1 or within the first week of C1 (results to be submitted to iRIS).

- **Arm 2 and Arm 3:** Thyroid function test (detailed in Section 7.6.3).

6.4.2. **Baseline Visit (Days –7 to Day 1)**

- Physical exam (Section 7.6.4), including height and weight. Measurements of height obtained within the previous 12 months may be used.
- Vital signs (Section 7.6.2)
- Pregnancy test for subjects of childbearing potential (serum or urine pregnancy test; see Section 7.6.5) – must be performed within 3 days prior to administration of LV
- ECOG performance status ([Appendix J](#))
- CBC with differential (see Section 7.6.3; results to be submitted to iRIS)
- Serum chemistry panel and liver function tests (see Section 7.6.3; results to be submitted to iRIS)
- Estimated GFR calculation (see Section 7.6.3; results to be submitted to iRIS)
- Collection of concomitant medication information
- Collection of AEs

6.4.3. **Treatment Cycle (Day 1 to Day 21)**

6.4.3.1. **Day 1**

If baseline visit activities occur within 3 days prior to C1 Day 1, the following assessments do not need to be repeated at the C1 Day 1 visit:

- Physical exam (Section 7.6.4) including weight
- ECOG performance status ([Appendix J](#))
- CBC with differential
- Serum chemistry panel and liver function tests
- Pregnancy test

Predose

- Confirm subject meets dosing criteria (Section 5.2.3.1)
- Physical exam (Section 7.6.4), including weight
- Pregnancy test (serum or urine) for subjects of childbearing potential (see Section 7.6.5) – does not need to be repeated if it has been performed within 3 days prior to administration of LV
- ECOG performance status ([Appendix J](#))

- Random blood glucose to be collected prior to dosing on Day 1 of each 21-day cycle (see Section 5.6; results to be submitted to iRIS)
- CBC with differential (see Section 7.6.3; results to be submitted to iRIS)
- Serum chemistry panel and liver function tests (see Section 7.6.3; results to be submitted to iRIS)
- **Arm 2 and Arm 3:** Thyroid function tests (detailed in Section 7.6.3); to include thyroid-stimulating hormone (TSH), T3 or free T3, and free T4). Day 1 of each odd-numbered cycle only (i.e. Cycles 1, 3, 5, 7, etc).
- Vital signs:
 - **Arm 1:** within 60 minutes prior to the start of LV infusion, see Section 7.6.2
 - **Arm 2 and Arm 3:** within 60 minutes prior to LV infusion, within 60 minutes prior to pembrolizumab infusion, see Section 7.6.2
- Blood samples for PK and ATA assessment (C1 to C5 and every 5 cycles thereafter, see Section 7.3 for time points)
- Blood samples for biomarker assessment (C1 to C6 only; see Section 7.4.1)
- Review CT/MRI, if applicable (see Section 7.2)
- **Arm 1, Arm 2, and Arm 3:** LV administration (a +4 day dosing window for Arm 1 and Arm 2 and a +2 day window for Arm 3) is allowed for subsequent dosing within a cycle; see Sections 5.2.3, 5.2.4.2, and 5.2.4.3. For nonclinical events requiring skipping a dose(s), must consult with and obtain approval by sponsor medical monitor. At least 7 days must elapse between administrations of LV.
- **Arm 2 and Arm 3:** Pembrolizumab will be administered 60–90 minutes following LV. For nonclinical events requiring skipping a dose(s), must consult with and obtain approval by sponsor medical monitor.

Postdose

- Vital signs:
 - **Arm 1:** within 30 minutes of ending each LV infusion, and during infusion as clinically indicated; see Section 7.6.2
 - **Arm 2 and Arm 3:** within 2 hours of ending each infusion, and during infusion/s as clinically indicated; see Section 7.6.2
- Blood samples for PK assessment (see Section 7.3 for time points)

6.4.3.2. Day 3

- Blood samples for PK assessment (visit window may be +1 day; C1 and C4 only, see Section 7.3)

6.4.3.3. Day 8 (\pm 2 days)

Predose

- Confirm subject meets dosing criteria (Section 5.2.3.1)
- Physical exam (Section 7.6.4) (C1 only)
- CBC with differential (see Section 7.6.3; results to be submitted to iRIS), Cycles 1 and 2 only
- Serum chemistry panel and liver function tests (see Section 7.6.3; results to be submitted to iRIS), Cycles 1 and 2 only
- Random blood glucose in Cycles 1 and 2. Following Cycle 2, random blood glucose may be collected as indicated in subjects at risk for hyperglycemia. (see Section 5.6; results to be submitted to iRIS)
- Vital signs (within 60 minutes prior to the start of LV infusion, see Section 7.6.2)
- Blood samples for PK assessment (C1 and C4 only; see Section 7.3 for time points)
- **Arm 1, Arm 2, and Arm 3:** LV administration (a +4 day dosing window for Arm 1 and Arm 2 and a +2 day window for Arm 3). See Sections 5.2.3, 5.2.4.2, and 5.2.4.3. For nonclinical events requiring skipping a dose(s), must consult with and obtain approval by sponsor medical monitor. At least 7 days must elapse between administrations of LV.

Postdose

- Vital signs:
 - **Arm 1:** within 30 minutes of ending each LV infusion, and during infusion as clinically indicated; see Section 7.6.2
 - **Arm 2 and Arm 3:** within 2 hours of ending each infusion, and during infusion/s as clinically indicated; see Section 7.6.2
- Blood samples for PK assessment (C1 and C4 only; see Section 7.3 for time points)

6.4.3.4. Day 15 (\pm 2 days)

Note: Subjects in Arm 1 and Arm 2 will require the following:

- CBC with differential (–2-day window; see Section 7.6.3; results to be submitted to iRIS), Cycles 1 and 2 only
- Physical exam (C1 only; see Section 7.6.4)

The following is for Arm 3 only:

Predose

- Confirm subject meets dosing criteria (Section 5.2.3.1)
- Physical exam (C1 only; see Section 7.6.4)
- CBC with differential (see Section 7.6.3; results to be submitted to iRIS), Cycles 1 and 2 only
- Serum chemistry panel and liver function tests (see Section 7.6.3; results to be submitted to iRIS), Cycles 1 and 2 only
- Random blood glucose in Cycles 1 and 2. Following C2, random blood glucose may be collected as indicated in subjects at risk for hyperglycemia. (see Section 5.6; results to be submitted to iRIS)
- Vital signs (within 60 minutes prior to the start of LV infusion, see Section 7.6.2)
- Blood samples for PK assessment (C1 and C4 only; see Section 7.3 for time points)
- Blood samples for biomarker assessment (C1 and C2 only; see Section 7.4.1)
- LV administration (a +2 day dosing window is allowed for subsequent dosing within a cycle; see Sections 5.2.3 and Section 5.2.4.2). For nonclinical events requiring skipping a dose(s), must consult with and obtain approval by sponsor medical monitor. At least 7 days must elapse between administrations of LV.

Postdose

- Vital signs (within 2 hours of ending each infusion, and during infusion(s) as clinically indicated; see Section 7.6.2)
- Blood samples for PK assessment (C1 and C4 only; see Section 7.3 for time points)

6.5. On treatment Response Assessments

Time points for radiographic exams for patients with RECIST v1.1 measurable tumor lesions or bone scan should be calendar based and do not depend on cycle visits. It is recommended that scans not be scheduled on the dosing day. It is recommended that scans done on the same day as Day 1 of subsequent cycles be completed and reviewed prior to infusion with LV.

The schedule of response assessments should not be adjusted for dose delays, dose interruptions, or other reasons for changes in the timing of a subject's study activities. Imaging should be conducted on the following schedule (Sections 6.5.1 and 6.5.2) until treatment is discontinued for any of the following reasons: disease progression, unacceptable toxicity, investigator decision, consent withdrawal, study termination by the sponsor, pregnancy, or death, whichever comes first. For all tumor cohorts, imaging should also be performed whenever disease progression is suspected.

6.5.1. For non-prostate cancer subjects (Cohorts 1–6, and 8):

- Every 6 weeks (± 3 days) for 12 months after the first dose of LV

- Every 12 weeks (± 7 days) thereafter

Objective responses (CR or PR) will be confirmed with repeat scans 4–6 weeks after the first documentation of response.

6.5.2. For prostate cancer subjects (Cohort 7):

- PSA assessment every 3 weeks (± 3 days) per calendar
- CT/MRI scan every 8 weeks (± 7 days) per calendar for the first 24 weeks, then every 12 weeks (± 7 days) thereafter
- Bone scan every 8 weeks (± 7 days) per calendar for the first 24 weeks, then every 12 weeks (± 7 days) thereafter

6.6. End of Treatment Visit (30 to 37 days after last dose of study drug)

Subjects will continue to receive LV until disease progression, unacceptable toxicity, investigator decision, consent withdrawal, study termination by the sponsor, pregnancy, or death, whichever comes first.

Regardless of time since last dose, EOT visits should be completed prior to administration of a new therapy. EOT visits should occur within 30 to 37 days after the last dose of LV unless delayed due to an AE. If EOT evaluations are completed before 30 days after the last study treatment, the subject will be contacted 30 to 37 days following the subject's last study treatment to assess for AEs and concomitant medications.

- Physical examination (Section 7.6.4), including weight
- Vital signs (Section 7.6.2)
- Pregnancy test for subjects of childbearing potential (see Section 7.6.5)
- ECOG performance status (Appendix I)
- CBC with differential (see Section 7.6.3; results to be submitted to iRIS)
- HbA1c (see Section 7.6.3; results to be submitted to iRIS)
- Serum chemistry panel and liver function tests (see Section 7.6.3; results to be submitted to iRIS)
- CT/MRI scan (see Section 7.2 for details); not required if previous scan was completed within 4 weeks prior to EOT
- Blood samples for PK and ATA assessment (see Section 7.3 for time points)
- Blood samples for biomarker assessment (see Section 7.4.1)
- For prostate cancer subjects:
 - PSA assessment (see Section 7.6.3)
 - Bone scan (see Section 7.2.1), not required if previous scan was completed within 4 weeks prior to EOT

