4.4.1. Discontinuation of Study Treatment

A subject's study treatment may be discontinued for any of the following reasons:

- Progressive disease (PD)
- AE
- Pregnancy
- Investigator decision
- Subject decision, non-AE

Note: Ensure that subjects who decide to stop treatment **because of an AE** are not included in this rationale.

- Study or cohort termination by sponsor
- Other, non-AE

Subjects who discontinue from study treatment will remain on study for follow-up unless they withdraw consent.

For Part C Arm 2 and Arm 3:

Patients who discontinue pembrolizumab may continue to receive LV with medical monitor approval. Similarly, patients that discontinue LV may continue to receive pembrolizumab with medical monitor approval. See Sections [5.2.4.3](#) and [5.3](#) for details.

Administration of pembrolizumab is limited to 35 cycles (approximately 2 years). The number of administrations is calculated starting with the first dose of pembrolizumab.

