5.3.4.3. Other Allowed Dose Interruption for Pembrolizumab

Pembrolizumab may be interrupted for situations other than treatment-related AEs such as medical/surgical events or unforeseen circumstances not related to study therapy. Patients should be placed back on study therapy within 3 weeks of the originally scheduled dose and within 42 days of the previously administered dose, unless otherwise discussed with the sponsor. The reason for interruption should be documented in the patient's study record.

Patients who discontinue LV due to an LV-related AE (see Sections 5.2.4.2 and 5.2.4.3) may continue pembrolizumab with approval of the medical monitor if there is evidence of clinical benefit. The maximum allowed number of pembrolizumab cycles is 35 (approximately 2 years).

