6.7. Follow-up

All subjects will be followed for survival until death or study closure, whichever occurs first. Survival and subsequent anticancer therapy follow-up may be conducted with clinic visits or telephone calls.

For subjects who discontinue study treatment for reasons other than progression, the following assessments will be conducted every 6 weeks (± 3 days) for 12 months after the first dose of LV and every 12 weeks (± 7 days) thereafter, until disease progression, initiation of a new anticancer therapy, investigator decision, consent withdrawal, study termination by the sponsor, pregnancy, or death, whichever comes first:

- Physical examination (see Section [7.6.4](#))
- Pregnancy test for subjects of childbearing potential 24 weeks after the last dose of LV (see Section [7.6.5](#))
- CT/MRI scan (see Section [7.2](#) for details); after a year of follow-up, reduce frequency to institution's standard of care
- In subjects who discontinue study treatment due to pregnancy, response assessments should be conducted as appropriate

For prostate cancer subjects who discontinue study treatment for reasons other than progression, the following assessments will be conducted until disease progression, initiation of a new anticancer therapy, investigator decision, consent withdrawal, study termination by the sponsor, or death, whichever comes first:

- Physical examination every 12 weeks (± 7 days) (see Section [7.6.4](#))
- PSA assessment every 12 weeks (± 7 days)
- Bone scan every 12 weeks (± 7 days) (see Section [7.2.1](#))
- Soft tissue tumor assessment (CT/MRI) every 12 weeks (± 7 days) until disease progression for subjects with measurable disease

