9.3.8.4. Clinical Laboratory Results

Summary statistics of laboratory results and changes from baseline will be tabulated by scheduled visit. Grading of laboratory values will be assigned programmatically per the NCI CTCAE v5.0. Shift tables comparing the worst post-baseline to baseline CTCAE grade will be presented. Laboratory values will be listed with grade per CTCAE and flagged when values are outside the normal reference range.

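### Protocol Section 6.6 times the end-of-treatment visit from the last LV dose, although Arm 2 and 3 subjects may stay on pembrolizumab after LV stops

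*Protocol*

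**What the plan says.** Protocol Section 6.6 times the EOT visit in more than one way.

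- Heading: "End of Treatment Visit (30 to 37 days after last dose of study drug".
- Body, the instruction to sites: "EOT visits should occur within 30 to 37 days after the last dose of LV unless delayed due to an AE".
- Next sentence: if EOT evaluations are done early, the subject is contacted 30 to 37 days after the "last study treatment to assess for AEs and concomitant medications".
- Opening sentence of the body: describes continued dosing in terms of LV only.

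Appendix D (both Part C tables) times the EOT column from the last dose without naming a drug; footnote a refers to the last study treatment.

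LV and pembrolizumab need not stop together. Section 4.4.1 says "patients that discontinue LV may continue to receive pembrolizumab with medical monitor approval". Section 5.3.4.3 says that subjects who stop LV for an LV-related AE "may continue pembrolizumab with approval of the medical monitor if there is evidence of clinical benefit". Sections 5.2.4.2 (Arm 3) and 5.2.4.3 (Arm 2) make the same allowance. Pembrolizumab is limited to 35 cycles in total.

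The EOT visit in 6.6 includes an examination, vital signs, CBC, HbA1c, "Serum chemistry panel and liver function tests (see Section 7.6.3; results to be submitted to iRIS", and PK and antitherapeutic-antibody (ATA) samples. Table 19 marks EOT samples for LV and pembrolizumab, both PK and ATA.

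**The concern.** In Parts A and B and in Part C Arm 1, LV is the only study treatment, so every anchor gives the same date. In Arms 2 and 3 they separate once LV stops and pembrolizumab goes on. A site that follows the body sentence then holds an end-of-treatment visit while protocol treatment continues, or shortly after the last pembrolizumab dose.

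Nothing later in the schedule replaces that visit. The contact 30 to 37 days after the last study treatment covers AEs and concomitant medications only. Section 6.7 begins "For subjects who discontinue study treatment for reasons other than progression, the following assessments will be conducted every 6 weeks" and lists an examination, a pregnancy test and scans, but no CBC, chemistry or liver tests.

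Safety of the combination is a secondary objective, and Section 5.3.4.1 notes that immune-related events can appear months after the last pembrolizumab dose. A laboratory check about a month after the end of all treatment therefore has a purpose. Two sites could also time the visit differently and both be compliant.

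**Working it through.** The plan states no figure to reproduce. The check is day arithmetic on the visit schedule.

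**Inputs**
- d = cycle day of the last LV dose: 1 or 8 in Arm 2; 1, 8 or 15 in Arm 3 (Section 5.1).
- m = number of pembrolizumab doses in later cycles, each on Day 1 of a 21-day cycle (Section 5.1).
- w = 0 to 7, the position within the 30-to-37-day window (Section 6.6).
- Days are counted from the start of the last LV cycle. Cycles are assumed to run on schedule.

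**Formulas**
- EOT visit under the LV sentence: day d + 30 + w.
- Last pembrolizumab dose: day 21m + 1.
- Visit minus last pembrolizumab dose: (d + 30 + w) − (21m + 1) = d + 29 + w − 21m.

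**Results** (lowest value at d = 1, w = 0; highest at d = 15, w = 7)

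| Further pembrolizumab doses | Lowest | Highest | Visit relative to last pembrolizumab dose |
|---|---|---|---|
| m = 1 | 1 + 29 + 0 − 21 = 9 | 15 + 29 + 7 − 21 = 30 | 9 to 30 days after |
| m = 2 | 1 + 29 + 0 − 42 = −12 | 15 + 29 + 7 − 42 = 9 | 12 days before to 9 days after |
| m = 3 | 1 + 29 + 0 − 63 = −33 | 15 + 29 + 7 − 63 = −12 | 33 to 12 days before |

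Each further dose moves the range 21 days earlier, so for m of 3 or more at least one dose always follows the visit. Arm 2 has no Day 15 LV dose, so its highest values use d = 8: 23, 2 and −19.

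If the visit were timed from the end of all treatment, the figure would be 30 to 37 days after the last dose in every row. The LV sentence reaches that window only at its edge (m = 1, d = 15, w = 7).

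**Subjects exposed.** Arms 2 and 3 plan 30 + 30 = 60 subjects. The documents give no rate of stopping LV alone, so the number affected lies between 0 and 60.

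**What does not move**
- AE and SAE reporting in Arms 2 and 3 runs to the later of the EOT visit or 90 days after the last study treatment (Section 7.6.1.3).
- CBC, chemistry and liver tests continue on Day 1 of each cycle (Section 6.4.3.1, Appendix D).
- Imaging follows the calendar (Section 6.5), so ORR, DOR and PFS do not depend on the EOT date.
- Thyroid tests are not an EOT assessment, so none are displaced.

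**The case against.** The best reply is that one LV-only phrase stands against everything around it. The visit is named for the end of treatment, the next sentence and Appendix D footnote a speak of the last study treatment, and Table 19 puts pembrolizumab samples at EOT. A sensible site would wait until both drugs had stopped. That is a fair account of the intent and limits how many sites would go wrong. But the only sentence that instructs sites on timing names LV, and no text says another anchor prevails.

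A second reply is that the sentence says should, not must, and allows delay for an AE, while Sections 5.2.4.2, 5.2.4.3 and 5.3.4.3 tie pembrolizumab alone to an LV-related AE. This weakens the claim that sites would be driven to an early visit. It does not settle the timing: delay for an AE is not a rule to wait for the last pembrolizumab dose, and Section 4.4.1 does not limit the allowance to AEs.

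A third concerns the heading. A reader might infer an outright contradiction between heading and body. Usage is mixed: Section 5.2 labels LV the investigational study drug, while Table 16, on pembrolizumab infusion reactions, uses study drug for pembrolizumab treatment. If study drug meant LV only, heading and body would agree, and the fault would be that Section 6.6 does not provide for pembrolizumab. The consequence for the visit would be the same.

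**Conclusion.** The point holds as a minor wording fault with a practical effect. Followed as written, the body of Section 6.6 places the EOT assessments and samples during pembrolizumab or soon after it, and leaves no scheduled laboratory check 30 to 37 days after the end of all treatment. The wording is certain. How many sites would follow it literally, and how many of the 60 subjects would stop LV alone, cannot be known from the documents. The visit-timing ranges assume on-schedule cycles and a site that follows the LV sentence.

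A reader might go further and infer that treatment duration and laboratory results would be cut short in the analysis, because SAP Sections 6.4 and 6.6.2 refer to the EOT visit. The documents do not support that. The SAP implements the original protocol of 22 April 2019, with a single arm and LV 2.5 mg/kg for all subjects; it does not cover Part C. An effect on duration would require its rules to be carried over unchanged, its study dose to include pembrolizumab, and sites to follow the LV sentence. The protocol text that does cover Part C has no EOT cut-off: Section 9.3.8.4 says "Summary statistics of laboratory results and changes from baseline will be tabulated by scheduled visit", and Section 9.3.8.1 sets none either.

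Nor does the plan lose on-treatment safety data. What is misplaced is one post-treatment visit and its samples. The pembrolizumab samples are archived for possible analysis only (Section 7.3).

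**What to change.** At the next protocol amendment:

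1. In the body of Section 6.6, time the visit from the last dose of LV or pembrolizumab, whichever is given last.
2. Make the opening sentence of 6.6 refer to study treatment instead of LV.
3. Use the same anchor in the EOT column of both Appendix D tables.
4. Align the last pregnancy test. Section 7.6.5 sets it 24 weeks after EOT, while Section 6.7 and Appendix D footnote e set it 24 weeks after the last LV dose. Moving the EOT visit later would widen that gap for these subjects, so one anchor should be chosen for all three places.

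The SAP update that Part C needs in any case should use the same EOT anchor; nothing more is required there.

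The cost is a few phrases of text. No subjects or procedures are added; the visit moves later for the subjects concerned.
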